*Survey and Randomization Procedures:* Separate surveys were conducted for parents and teens at baseline (at time of enrollment), and at 6, 12 and 18 months later. After both parent and teen completed the baseline survey, families were randomly assigned to either the intervention or control condition using a computer-generated program. Automated e-mails and texts were sent to invite families to complete the follow-up surveys. One week after follow-up survey invitations were sent, reminder e-mails and texts were sent to families who had not completed the surveys, with the e-mails/texts repeated after another week of nonresponse. One week later, separate phone calls were made to parents and teens if they had still not completed. Participants could complete the surveys up to 2 months after surveys were initiated. Of the 411 enrolled dyads, 315 teens (76.6%) and 364 parents (88.6%) completed the 6-month follow-up surveys, and 311 teens (75.7%) and 354 parents (86.1%) completed the 12-month follow-up surveys and 309 teens (75.2%) and 357 parents (86.9%) completed the 18-month follow-up surveys.

*Measures:* Measurement of assignment to condition (experimental vs. control) was based upon the original randomized assignment. Program dosage (no exposure, exposure to alcohol component, exposure to relationship component) was based upon tracking progress through the program, automated in the online delivery.

*Teen alcohol use.* Alcohol items were adapted from the National Longitudinal Study of Adolescent Health (Harris et al., 2008) and asked in surveys. Teens first reported whether they had consumed alcohol over the past 6 months and past 30 days (1 = Yes, 0 = No).

*Quantity and frequency of alcohol use.* Teens reported their frequency of drinking over the past 30 days and past 6 months (0 = Never, 1 = once a month, 2 = 2–3 times a month, 3 = once a week, 4 = 2–3 times a week, and 5 = daily or almost daily). The variable was recoded to more closely approximate the actual number of times used over the time period. For example, 2–3 times a month in the last 30 days was recoded to 2.5, whereas 2–3 times a month over the past 6 months was recoded to 15 (2.5 = 6 months). Teens also reported the usual amount they drank on drinking days (0 = less than one to 7 = more than six).

*Drunkenness:* To assess drunkenness, teens reported the number of times they had gotten “drunk or very, very high” on alcohol over the time period (e.g., past 6 months, past 30 days).

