### **Analyses:**

Descriptive analyses were conducted first to describe rates and mean scores of outcomes overall and by condition across three assessments to check the randomization.

Selection model: Because families chose how much of the intervention to which they were exposed, we conducted a probit analysis predicting whether or not a family completed the alcohol or relationship component from baseline measures. Based on this analysis, an instrumental variable, inverse Mills’ ratio (IMR) representing the underlying selection processes was included as a covariate in our primary dosage analyses (Heckman, 1979). The IMR (non-selection hazard) was calculated in Stata using the two-step procedure described in Heckman (1979). When the IMR is significant in a model, this indicates that the predicted probability of completing the component is associated with the outcome. That is, the same factors that predispose families to complete (or not complete) the component are related to the outcomes. In models where dosage is significant, this indicates that even accounting for factors that are related to completing the program, that dosage is still related to outcomes.

Conducting analyses in SPSS 21, dichotomous outcomes were examined using multiple logistic regression, while continuous outcomes were examined using multiple linear regression. Listwise deletion was used for missing cases. For all regression analyses, the baseline value of the outcome variable, teen gender, teen age, and teen ethnicity, an inverse Mills’ ratio and intervention condition, were covariates to determine whether dosage predicted the outcome for a specific follow-up period (i.e., 6, 12 18 months).

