### **Assessment of Efficacy-Overview:**

Results from the Smart Choices 4 Teens program indicate efficacy for prevention of alcohol use and alcohol-related problem behaviors for older teens when parents and teens, with greater exposure to the program content producing better outcomes, when controlling for baseline rates and selection bias. The intervention also showed efficacy for parent–teen communication, especially around conversations related to social host laws. Further parents and teens engaged in the program were less likely to discuss ways that teens could drink “safely,” and thus not providing a message that teens could drink if they drank safely. Of particular importance is that the dosage effects were noted across different alcohol involvement indicators and some of these impacts persisted at the 12-month follow-up period, showing that the program may have sustained effects.

For the relationships/sexual behaviors component of the intervention, the data support the efficacy of the Smart Choices 4 Teens intervention in increasing adolescent and parent communications about sexual relationships (eg, frequency) and to increase parental guidance (eg, dating rules) when controlling for baseline rates and selection bias. There was some support that the intervention had a main effect on frequency of communication and dating rules set for the adolescents, even after controlling for other adolescent characteristics that were also significant predictors of adolescents’ reports of sexual communication with their parents, including developmental changes over time, as well as adolescent gender, sexual minority status, and sexual experience.

There were indications that the intervention had impact on sexual communication over time, irrespective of the gender of the adolescent. When accounting for the possible interaction between the time of administration, gender of the adolescent, and exposure to the intervention, demonstrated an impact on the parent-teen sexual communication outcome. The intervention increased parent-teen communications regarding increased dating rules, indicating greater parental monitoring of teen relationships. There was no indication of an interaction effect between gender and intervention exposure on dating rules. Participating in the intervention increased the dating rules for all participants and was durable across time.

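### Efficacy is claimed from dozens of outcome-by-wave tests with no stated primary outcome, primary wave, significance level or multiplicity rule, and the alcohol claim rests on self-selected exposure

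*Combined protocol and SAP*

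**What the plan says.** The Purpose of Study section sets an aim in two domains, alcohol use and sexual behaviour. The Measures text lists outcomes in both and ranks none of them.

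The Analyses section fits logistic or linear regressions to determine "whether dosage predicted the outcome for a specific follow-up period (i.e., 6, 12 18 months"). The word primary is attached there only to a class of models: the inverse Mills' ratio "was included as a covariate in our primary dosage analyses". The reason given for the ratio is self-selection: "Because families chose how much of the intervention to which they were exposed". The reading rule begins "In models where dosage is significant, this indicates that even accounting for factors that are related to completing the program" and ends by saying that dosage is still related to the outcome. No threshold for significance is given; the alpha values in the Measures text are scale reliabilities.

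The Assessment of Efficacy overview then claims efficacy for alcohol use and related problem behaviours, "with greater exposure to the program content producing better outcomes, when controlling for baseline rates and selection bias". It adds that "the dosage effects were noted across different alcohol involvement indicators and some of these impacts persisted at the 12-month follow-up period". For the relationship component it says that "the data support the efficacy of the Smart Choices 4 Teens intervention in increasing adolescent and parent communications about sexual relationships", and it cites, with hedging, a main effect of the intervention on communication frequency and dating rules.

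**The concern.** Two gaps compound each other.

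- **Multiplicity.** With many outcomes, up to three waves each and no ranking, any significant coefficient can be carried into the conclusion. The overview says that some alcohol effects persisted at 12 months without saying which. It mentions neither 18-month alcohol use nor any result for sexual activity, although both were measured. A reader cannot separate claims that would survive an error-control rule from claims picked out of a large set.
- **Basis of the claim.** Condition "was based upon the original randomized assignment", so a randomised comparison is available. The alcohol conclusion is instead worded around exposure, and in causal terms. In the Analyses section condition enters only as a covariate alongside dosage. Dosage arises after randomisation, so the condition coefficient in that model is not the plain randomised contrast.

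At stake is whether the word efficacy describes a confirmatory, randomised finding or a selected association.

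**Working it through.** The documents give no alpha, power or family-wise error figure, so there is no design figure to reproduce.

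**Step 1. Count the tests (Measures text; waves from Analyses).** The documents do not list the models fitted, so these counts are reconstructions.

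- Alcohol use, 7 outcomes: any use in 2 recall windows, frequency in 2 windows, usual amount, drunkenness in 2 windows. Over 3 waves: 7 × 3 = 21.
- Alcohol communication: 3 constructs × 2 reporters = 6. The Measures text lists follow-up at 6 and 12 months: 6 × 2 = 12.
- Sexual behaviour and communication, 5 outcomes: communication frequency, delaying sex, health risks, dating rules, sexual activity. Over 3 waves: 5 × 3 = 15.

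| Reading | Count |
|---|---|
| Low: one recall window, one reporter, one model over time per relationship outcome | 4×3 + 3×2 + 5 = 23 |
| Alcohol use at two follow-ups only | 14 + 12 + 15 = 41 |
| Alcohol use at three follow-ups | 21 + 12 + 15 = 48 |
| High: 8 alcohol-use outcomes, three waves throughout | 24 + 18 + 15 = 57 |

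The high reading gives alcohol communication a third wave that the Measures text does not list, so it is an upper case. Sex-topic items, condition coefficients and interactions are not counted in any row.

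**Step 2. Family-wise error.** Assume two-sided 5% per test and all null hypotheses true. Under independence, P(at least one false positive) = 1 − 0.95^k, and the expected number is 0.05k.

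| k | P(at least one) | Expected number |
|---|---|---|
| 14 (alcohol use, 6 and 12 months) | 51% | 0.70 |
| 21 (alcohol use, all waves) | 66% | 1.05 |
| 23 | 69% | 1.15 |
| 41 | 88% | 2.05 |
| 48 | 91% | 2.40 |
| 57 | 95% | 2.85 |

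**Step 3. Allow for correlation.** These outcomes overlap, so independence overstates the problem. Simulating equally correlated normal test statistics, with correlation from 0.3 up to 0.8, gives 44% down to 20% for 14 tests, 55% down to 23% for 21, and 80% down to 30% for 48. Every figure is well above 5%.

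**Step 4. Compare the wording.** The Analyses section interprets a significant dosage coefficient as a relation that remains after adjustment for selection. The overview describes the same class of result as effects, as exposure producing better outcomes, and as efficacy. The change from association to efficacy occurs between the two sections, and no decision rule in the text licenses it.

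**The case against.** The strongest reply has four parts.

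1. **The Analyses section is more careful than the overview.** This stands. It speaks of a relation, not an effect, so the overstatement belongs to the overview alone.
2. **The overview hedges and does not rest on dosage throughout.** This also stands. A reader might infer that every efficacy claim comes from a dosage coefficient. The text does not support that: for communication frequency and dating rules it cites some support for an intervention main effect. That claim still lacks a multiplicity rule, and the only condition term the Analyses section describes sits in a model that also contains dosage.
3. **The count of tests is uncertain.** True: it depends on the number of alcohol-use waves, recall windows and reporters. The conclusion does not depend on which count is right, since even 14 tests at a correlation of 0.8 give about 20%.
4. **Details are referred to an online report and publications.** An overview need not carry p-values, and their absence here is not itself the defect. Estimates published elsewhere would not, however, supply a ranking or an error-control rule in this plan.

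It also stands that each test may have had a nominal per-test level. What is missing is control over the set of tests.

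**Conclusion.** The point holds. The visible text contains no primary outcome, primary wave, significance level or multiplicity rule, and the overview makes efficacy claims from roughly 23 to 57 implied tests. Family-wise error is uncontrolled: about 66% for the 21 alcohol-use tests and 91% for 48 under independence, or 23–55% and 30–80% at correlations of 0.3 to 0.8. The 5% level, the correlations and the counts are assumptions. For alcohol, the claim also has a non-randomised basis.

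Two stronger inferences are tempting, and neither is supported. A reader might conclude that the reported effects are false; a high family-wise error rate under the null does not show that. A reader might instead count the favourable results in the overview and conclude that chance cannot explain them. The documents give neither the number of tests nor the number that were significant, so that comparison cannot be made reliably.

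**What to change.** Using the data already collected:

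1. For every listed outcome and wave, fit the randomised-condition contrast with the baseline covariates named in Analyses (baseline value of the outcome, teen gender, age and ethnicity), but without the dosage and inverse Mills' ratio terms. Report the estimate, interval and p-value for each, including 18-month alcohol use and sexual activity.
2. State a 5% level and apply Holm within two families, alcohol and sexual behaviour/communication, over the outcome-by-wave tests. State that families set after the results are known limit the claims but do not restore prospective error control.
3. In the overview, keep efficacy only for condition contrasts that survive in the program's favour. Call dosage results associations, and label all other results exploratory.

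The cost is re-analysis, rewording and lower power per test. On the 48-test reading the families hold 21 + 12 = 33 and 15 tests, so the first Holm thresholds are 0.05/33 = 0.0015 and 0.05/15 = 0.0033. A test with 80% power at 5% has noncentrality 1.960 + 0.842 = 2.802. Its power at those thresholds is Φ(2.802 − 3.172) = 36% and Φ(2.802 − 2.935) = 45%; later Holm steps are less strict. Two families at 5% each allow up to 10% overall. Some claims in the overview will become exploratory.

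The overview's relationship results mention adjustment variables that are not in the Analyses covariate set. That is a separate matter and should be raised on its own.

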*Conversations regarding delaying sex until older:* Three items asked whether a parent had cautioned the adolescent not to have sex, not to have a serious relationship in high school, and not to have sex specifically because their religion or values forbid sex outside of marriage. A sum of the three items was taken, and reliability was adequate (T0:  $\alpha = .62$ ; T1:  $\alpha = .64$ ; T2:  $\alpha = .68$ ; T3:  $\alpha = .70$ ).

*Health risks associated with sex:* Two items were summed for discussions of health risks: “sex can result in pregnancy” and “sex can result in a sexually transmitted infection.” The two items were significantly correlated for all four waves (T0:  $r^2 = 0.58$ ;  $P < .001$ ; T1:  $r^2 = 0.71$ ;  $P < .001$ ; T2:  $r^2 = 0.74$ ;  $P < .001$ ; T3:  $r^2 = 0.77$ ;  $P < .001$ ).

*Parental monitoring and dating rules:* Adolescents were each asked about the expectations for behavior in romantic relationships that they had decided upon (Madsen, 2008). They were asked to respond no (0) or yes (1) to a list of 15 possible rules, for example, “no dates on school nights,” “come home at an agreed-upon time (curfew),” “use good judgment,” and “be a gentleman/lady.” Responses were summed. Internal consistency was good (T0:  $\alpha = .83$ ; T1:  $\alpha = .87$ ; T2:  $\alpha = .86$ ; T3:  $\alpha = .89$ ).

*Sexual activity:* Teens were asked whether they had had sex at baseline (ever), and at 6, 12, 18 month follow-up surveys (during the past 6 months) with answers of Yes/No.

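### The relationship-component main effect comes from a longitudinal model that the analysis section does not describe, and the time point of its sexual-experience covariate is not stated

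*Combined protocol and SAP*

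**What the plan says.** The Analyses section sets the covariates in one sentence: "For all regression analyses, the baseline value of the outcome variable, teen gender, teen age, and teen ethnicity, an inverse Mills’ ratio and intervention condition," are entered "to determine whether dosage predicted the outcome for a specific follow-up period (i.e., 6, 12 18 months". The model types are equally specific: "dichotomous outcomes were examined using multiple logistic regression, while continuous outcomes were examined using multiple linear regression", with listwise deletion. No time term, interaction or repeated-measures structure is mentioned.

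The Assessment of Efficacy-Overview reports some support for a main effect of the intervention on communication frequency and dating rules. It says this held after control for other predictors, among them change over time and "adolescent gender, sexual minority status, and sexual experience". It then describes a result obtained "When accounting for the possible interaction between the time of administration, gender of the adolescent, and exposure to the intervention", reports no gender-by-exposure interaction on dating rules, and calls the dating-rules effect durable over time.

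On the covariate itself, the Measures text under Study Design says: "Teens were asked whether they had had sex at baseline (ever), and at 6, 12, 18 month follow-up surveys (during the past 6 months". No measure is named sexual experience, and sexual minority status has no entry in the Measures at all. The Purpose of Study section names sexual behaviors among the things the program is meant to improve.

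**The concern.** Two current sections describe different analyses. A reader cannot trace the main-effect statement to the stated method, reproduce it, or tell whether the extra terms were chosen before the data were seen.

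The sexual-experience covariate matters more than the other additions. The question was repeated after randomisation and concerns behavior the program tries to change. If a follow-up answer was the covariate, the model holds fixed something the intervention may have altered. The condition coefficient then no longer measures the whole effect of being assigned to the program.

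**Working it through.** **Step 1. The two sections side by side.**

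| Feature | Analyses | Assessment of Efficacy-Overview (relationship component) |
|---|---|---|
| Effect tested | Dosage, with condition as a covariate | Intervention main effect |
| Time | One follow-up at a time | Change over time in the model; durability claimed |
| Gender | Covariate | Covariate, and in interactions |
| Age, ethnicity | Covariates | Not mentioned |
| Baseline outcome, selection term | Covariates | Control for baseline rates and selection bias mentioned |
| Sexual minority status | Not listed | Covariate |
| Sexual experience | Not listed | Covariate |
| Interactions | None | Time, gender and exposure; gender by exposure on dating rules |

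Separate regressions can show an effect at each wave, but they contain no term that compares waves. The time and durability statements therefore need a model that is not described. Such a model uses several records per teen: 315 + 311 + 309 = 935 completed teen follow-up surveys from at most 411 teens. Nothing says how the correlation within a teen was handled.

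**Step 2. Does the condition coefficient of the stated model supply the main effect?** No. The Exposure to Treatment section says 42.7% of intervention families completed the relationship materials, so 100 − 42.7 = 57.3% did not. If dosage enters as component completion, the condition coefficient in the same model compares those non-completers with controls. Completion was the family's choice, so this is not the randomised contrast.

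**Step 3. What the choice of sexual-experience value could do.** The documents give no figure to reproduce, so every input here is an assumption. There were 1,000,000 simulated teens per scenario, with T the arm (1:1) and U a standard normal shared cause:

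- Baseline activity: logit P(S0 = 1) = −0.5 + uU
- Follow-up activity: logit P(S1 = 1) = −1 + 2·S0 + bT + uU
- Outcome: Y = 0.2T + g·S1 + uU + noise (SD 1)

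The table gives the coefficient of T from least squares. Shifts were taken before rounding.

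| b (log odds ratio) | g | u | Adjusted for S0 | Adjusted for S0 and S1 | Shift |
|---|---|---|---|---|---|
| 0 | 0.2 or 0.5 | 0 or 0.5 | 0.197 to 0.202 | 0.197 to 0.202 | 0.00 |
| −0.3 | 0.2 | 0 | 0.190 | 0.201 | +0.011 |
| −0.3 | 0.2 | 0.5 | 0.191 | 0.214 | +0.023 |
| −0.3 | 0.5 | 0 | 0.171 | 0.200 | +0.029 |
| −0.3 | 0.5 | 0.5 | 0.171 | 0.211 | +0.040 |
| −0.6 | 0.2 | 0 | 0.178 | 0.200 | +0.023 |
| −0.6 | 0.2 | 0.5 | 0.182 | 0.227 | +0.045 |
| −0.6 | 0.5 | 0 | 0.144 | 0.201 | +0.057 |
| −0.6 | 0.5 | 0.5 | 0.144 | 0.221 | +0.077 |

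Adjusting for S0 alone left the unadjusted estimate unchanged to within 0.001. With u = 0 the shift equals −g times the change in activity that the program causes. Reversing the sign of g therefore reverses the shift: +0.011 becomes −0.011.

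**The case against.** The strongest reply has four parts.

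- **The leading efficacy sentence fits the stated method.** The relationship paragraph opens by claiming efficacy with control for baseline rates and selection bias, which matches two elements of the Analyses section. The unlisted covariates come in a second, hedged sentence. This stands: the whole relationship conclusion cannot be said to come from an undescribed model, only the main-effect, interaction and durability statements.
- **Omission is not exclusion.** The covariate sentence serves the dosage question, and further details are left to publications. This also stands. Even so, the sentence claims to cover all regressions, and the document describes no second model.
- **Sexual experience may be the baseline item.** It is listed beside gender and sexual minority status as a characteristic of the adolescent, and the baseline question about ever having had sex fits the term well. A reader might infer that the analysis did adjust for a post-randomisation variable and that the reported effects are inflated. The documents do not support that, because they never say which value was used.
- **Selective modelling is conjecture.** A reader might infer that terms were added afterwards to obtain a favorable result. Nothing in the text shows this, and one reported interaction is null. All that can be said is that prespecification is not documented.

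**Conclusion.** The mismatch is established from the text: the main-effect, interaction and durability statements for the relationship component rest on a model that the plan does not describe, with one covariate left undefined and another undated.

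The bias is conditional. It is absent if sexual experience is the baseline answer. It was also zero in the illustration when the program did not change sexual activity, and the relationship paragraphs of the efficacy overview report no such change. If a follow-up answer was used and the program did change activity, the estimate departs from the total randomised effect. The range of 0.00 to about 0.08 shows the mechanism under assumed inputs. It is not an estimate for this trial, and no percentage inflation can be given. The point merits correction because the statements support an efficacy conclusion and the remedy needs no new data.

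**What to change.** 1. Report communication frequency, topics and dating rules first as the effect of condition as randomised, adjusted for baseline covariates only. Leave dosage out of this model; the selection term belongs with the dosage analysis.
2. If sexual experience is kept, use only the baseline question on ever having had sex. Define sexual minority status in the Measures and use its baseline value.
3. Describe the longitudinal model in the Analyses section: covariates, time terms, interactions, and how repeated waves per teen are handled. Label it a sensitivity analysis unless it can be shown to have been prespecified.
4. Label the interactions involving time, gender and exposure exploratory.
5. Limit the main-effect and durability statements in the efficacy overview to what the randomised comparison shows.

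The cost is some re-analysis of existing data and rewording of the two sections. The reported effect may change, in a direction that cannot be predicted from the documents.

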### Sample Characteristics:

Among enrolled families at baseline, parents were on average 43.7 years of age ( $SD = 6.7$ ) and their teens were 16 or 17 years of age ( $M = 16.4$ ,  $SD = 0.5$ ). Mothers comprised 84.7% of the parents and slightly more than half (55.3%) of the teens were females. Household size ranged from two to 12 ( $M = 4.5$ ,  $SD = 1.6$ ). About one-tenth (9.5%) of the teens were Hispanic/Latino.

Teens reported the following race/ethnicities: 72.5% White, 1.9% Asian, 11.7% African American, 1.0% Native American, 8.3% Multiracial, 2.7% some other race, and 1.9% unreported. No significant differences were found between the experimental and control conditions on demographic characteristics at baseline.

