### **Exposure to Treatment**

Concerns about Recruitment: Because the intervention is available online, families could complete the intervention in their own homes, at a time convenient for them. Thus, some of the typical barriers to participation were removed. Despite these barrier reductions, only half (49.5%) of the families assigned to the intervention condition completed the program materials on teen alcohol use and less than half (42.7%) completed the materials on romantic/sexual relationships.

There are many reasons for prevention strategies to fall short of this total “inoculation” of the general population. First, families whose teens are perceived as “doing fine” or “not in need of any prevention” are difficult to engage in prevention. Second, parents sometimes believe that it is important not to prevent risky behaviors of teens like drinking and sexual activity but rather to teach teens how to engage in these behaviors while minimizing risks; they may not view a prevention program as aligned with their parental values. Third, families with teens who are already engaged in heavy alcohol consumption and/or engaged in risky sexual behaviors need a more intensive treatment intervention. Fortunately, there does not need to be total saturation of the general population for community-level perspectives to change. Nonetheless, an efficacious intervention that reaches even a sizeable proportion of the general population does potentially provide a resource to a sizeable number of families. Furthermore, parents of older teens do express a desire for some support and help in managing these “adult” behaviors.

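### The finding of no gender interaction on dating rules does not support a conclusion that the rules increased for all participants

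*Combined protocol and SAP*

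**What the plan says.** The third paragraph of the Assessment of Efficacy-Overview states: "There was no indication of an interaction effect between gender and intervention exposure on dating rules". The next sentence reads: "Participating in the intervention increased the dating rules for all participants and was durable across time". The paragraph before is more guarded. It claims only some support for a main effect on communication frequency and dating rules.

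The overview gives no estimate, standard error, confidence interval or p-value for the interaction, and no effect for girls or for boys. It refers readers to an online report and publications for detail.

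The Analyses section describes a separate regression for each follow-up, with teen gender listed as a covariate. It mentions no gender-by-intervention term, no margin for calling effects similar and no power for an interaction. The stated aim of those regressions is to test whether dosage predicts the outcome, with intervention condition as a covariate.

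On uptake, Exposure to Treatment reports that "less than half (42.7%) completed the materials on romantic/sexual relationships" among families assigned to the intervention.

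**The concern.** Failing to detect an interaction supports one statement: no difference in effect between girls and boys was detected. It does not show that the effects are equal, or that each gender benefited. The second sentence nevertheless makes a statement about everyone, and nothing in the section supports that step. A tentative average effect in one paragraph becomes a definite and general one in the next.

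What is at stake is what the trial may conclude about girls and boys separately. If the increase in dating rules came wholly or mostly from one gender, the reported facts could look just as they do now, and a reader would still take away that both benefit.

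There is also an ambiguity about the comparison. The overview uses exposure, participation and main effect without saying whether the dating-rules result compares randomised arms or compares families by how much they completed. With 42.7% completing the relationship materials, these are different comparisons, so it is unclear to whom the sentence applies.

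**Working it through.** The documents state no power or precision for this test, so there is no figure of theirs to reproduce. The check asks how much a null interaction could rule out.

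**Inputs from the documents**
- Teens at 18 months, from Survey and Randomization Procedures: "309 teens (75.2%) and 357 parents (86.9%) completed the 18-month follow-up surveys". So N = 309, the smallest of the three follow-ups (315, 311, 309).
- Gender split, from Sample Characteristics: "slightly more than half (55.3%) of the teens were females". So p = 0.553 girls and 0.447 boys.
- Completion of the relationship materials: 42.7% of intervention families.

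**Assumptions**
- Equal arms. The text says only that "families were randomly assigned to either the intervention or control condition using a computer-generated program" and gives no ratio.
- The baseline gender split holds in each group at follow-up, with a common SD. No SD is given for the dating-rules score, so results are in SD units.
- Covariates explain a share R² of the variance, from 0 to 0.5.
- Two-sided 5% level; 80% power for detectable differences (1.96 + 0.84 = 2.80).

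**Step 1. Ratio of standard errors.** With a the proportion in the exposed group:
- SE(main) = sqrt[(1 − R²) / (N·a·(1 − a))]
- SE(interaction) = sqrt[(1 − R²) / (N·p·(1 − p)·a·(1 − a))]
- Ratio = 1/sqrt(0.553 × 0.447) = 2.01

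N, R², the SD and the allocation ratio all cancel.

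**Step 2. Precision by assignment, one follow-up (a = 0.5, N = 309).**

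| R² | SE main | SE interaction | 95% half-width | Detectable difference, 80% power |
|---|---|---|---|---|
| 0 | 0.114 | 0.229 | 0.45 SD | 0.64 SD |
| 0.25 | 0.099 | 0.198 | 0.39 SD | 0.55 SD |
| 0.5 | 0.080 | 0.162 | 0.32 SD | 0.45 SD |

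For R² = 0: 309 × 0.553 × 0.447 × 0.25 = 19.10; sqrt(1/19.10) = 0.229; 1.96 × 0.229 = 0.45; 2.80 × 0.229 = 0.64. The detectable main effect is 0.32 SD at R² = 0 and 0.23 SD at R² = 0.5. Power for a true girl-boy difference of 0.3 SD is 26% to 46%.

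**Step 3. Averaging three follow-ups.** Assume a within-teen correlation r of 0.4 to 0.7. The variance is multiplied by f = (1 + 2r)/3 and, with baseline adjustment, by a further 1 − r²/f. The half-width runs from 0.25 SD (r = 0.7, adjusted) to 0.40 SD (r = 0.7, unadjusted).

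**Step 4. Exposure defined as completion.** With equal arms, a = 0.427 × 0.5 = 0.2135, comparing completers with everyone else. At one follow-up the half-width is 0.39 to 0.55 SD, and power for a 0.3 SD difference is 19% to 33%.

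**Step 5. An effect in one gender only.** Suppose the average effect lies at z = 2.
- All in girls: expected interaction z = (2/0.553)/2.01 = 1.80. The test misses it with probability of about 56%.
- All in boys: (2/0.447)/2.01 = 2.2, missed about 40% of the time.

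This step uses only the ratio from step 1, so it does not depend on the assumed SD, R², N or allocation.

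**The case against.** The best defence is that the sentence is conditional on participating and directly follows the gender result. Read that way, 'all participants' means both genders among those who took part, and the sentence is a loose way of saying that the effect did not depend on gender. That reading is fair, but it does not rescue the sentence, because benefit in both genders is exactly what a null interaction fails to show.

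Several stronger readings are tempting, and the documents do not support them.

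- **That non-completion refutes the sentence.** A reader might set 'all participants' against the 57.3% of intervention families (100 − 42.7) who did not complete the relationship materials. Given the condition on participating, the phrase need not cover every assigned family. Not completing is not the same as no exposure: the components were sequential, and some of these families may have done earlier components or part of this one. An average effect by assignment can also exist with partial uptake. The 42.7% matters here only because it makes the definition of exposure important.
- **That the authors expressly derived the claim from the null test.** The two sentences are adjacent, but no link is stated.
- **That the test has been shown to be too imprecise.** No standard error or interval is reported. The ±0.45 SD figure is the widest of the by-assignment cases. A three-way term with time is mentioned for sexual communication, which suggests that waves may have been modelled together, and that would narrow the interval. The ranges above allow for this, but they remain conditional on assumptions.
- **That gender-specific results do not exist.** The section is an overview and points elsewhere for detail. One can say only that they are not given here.

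It is also fair to say that dating rules are an intermediate parenting measure, and that the remedy changes reporting and not the design.

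**Conclusion.** The point holds in a limited form. The general conclusion about dating rules goes beyond the evidence in the section, which supports at most an average effect with no gender difference detected.

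The firmest part is the ratio of standard errors, 2.01, which needs only the 55.3% split and a similar gender mix and variance across groups. With it, an effect confined to one gender, and just large enough on average to reach significance, would go undetected roughly 40% to 56% of the time. The half-widths by assignment (about 0.32 to 0.45 SD at one follow-up, about 0.25 to 0.40 SD averaged over three) rest on the assumptions listed. Over that range a null result leaves room for little or no effect in girls or in boys.

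None of this shows that the effects do differ by gender, or that the average effect is absent. A reader should not infer either.

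**What to change.** In the Assessment of Efficacy-Overview:

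1. Delete 'for all participants'. Conclude only that no difference in effect by gender was detected, and add that this does not establish equal effects.
2. Report the interaction estimate with its 95% confidence interval, and the effect in girls and in boys, each with its interval.
3. State whether exposure and participating mean randomised assignment or completion of the relationship component. Word the average effect to match. It should be described as an effect among teens assigned to the intervention only if the analysis was by assignment; otherwise a dosage result would be relabelled as a randomised one.

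In the Analyses section, add the gender-by-intervention term to the models described, since gender now appears there only as a covariate.

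The cost is some wording plus a few estimates from a model that, on the overview's account, has already been fitted. The downside is a less sweeping claim.
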